17.2.1. Delegation of Responsibility

When specific tasks are delegated by an investigator, including but not limited to conducting the informed consent process, the Principal Investigator is responsible for providing appropriate training and adequate supervision of those to whom tasks are delegated. The investigator is accountable for regulatory violations resulting from failure to adequately supervise the conduct of the clinical study.

17.3. Institutional Review Board

Prior to gaining Approval-to-Enroll status, the investigational site will provide to the sponsor documentation verifying that their IRB is registered or that registration has been submitted to the appropriate agency, as applicable according to national/regulatory requirements.

A copy of the written IRB approval of the protocol (or permission to conduct the study) and Informed Consent Form, must be received by the sponsor before recruitment of subjects into the study. Prior approval must also be obtained for other materials related to subject recruitment or which will be provided to the subject.

Annual IRB approval and renewals will be obtained throughout the duration of the study as required by local/country or IRB requirements. Copies of the Investigator's reports and the IRB continuance of approval must be provided to the sponsor.

17.4. Sponsor Responsibilities

All information and data sent to BSC concerning subjects or their participation in this study will be considered confidential by BSC. Only authorized BSC personnel or a BSC representative including, but not limited to Contract Research Organization (CRO) will have access to these confidential records. Authorized regulatory personnel have the right to inspect and copy all records pertinent to this study. Study data collected during this study may be used by BSC for the purposes of this study, publication, and to support future research and/or other business purposes. All data used in the analysis and reporting of this study will be without identifiable reference to specific subject name.

Boston Scientific will keep subjects' identifiable health information confidential in accordance with all applicable laws and regulations. Boston Scientific may use subjects' health information to conduct this research, as well as for additional purposes, such as overseeing and improving the performance of its device, new medical research and proposals for developing new medical products or procedures, and other business purposes.

18. Monitoring

Monitoring will be performed during the study to assess continued compliance with the protocol and applicable regulations. In addition, the clinical research monitor verifies that study records are adequately maintained, that data are reported in a satisfactory manner with respect to timeliness, adequacy, and accuracy, and that the Principal Investigator continues to have sufficient staff and facilities to conduct the study safely and effectively. The Principal Investigator/institution guarantees direct access to original source documents by BSC personnel, their designees, the IRB, and appropriate regulatory authorities.

The study may also be subject to a quality assurance audit by BSC or its designees, as well as inspection by the IRB and/or appropriate regulatory authorities. It is important that the Principal Investigator and relevant study personnel are available during on-site monitoring visits or audits and that sufficient time is devoted to the process.

19. Potential Risks and Benefits

19.1. *Anticipated Adverse Events*

The following anticipated adverse events (AE) have been identified for this study.

Very Common:

- Minor bruising
- Post-operative pain and swelling

Common:

- Nausea associated with anesthesia

Less Common:

- Infection such as cellulitis or subcutaneous abscess
- Pain

Uncommon:

- Swelling
- Worsened back pain

Rare:

- Abnormal healing or failure to heal
- Allergic, immune, or inflammatory response or reaction to medication or surgical materials

- Death
- Deep vein thrombosis/thrombophlebitis
- Depression due to unmet expectations of treatment
- Dural tear with or without CSF leak
- Headache
- Hematoma of a serious type, e.g. an epidural hematoma resulting in paralysis
- Hemorrhage requiring transfusion
- Infection that is severe or life-threatening, such as epidural abscess, meningitis or sepsis
- Nerve injury, which can result in symptoms such as tingling, numbness, pain, loss of bladder or bowel control, weakness, or paralysis
- Pneumothorax, Pneumocephalus, or injury to other tissues during surgery
- Pulmonary embolism
- Radiation exposure (harm from this is rare)
- Respiratory arrest, e.g. apnea during surgical procedure
- Risks associated with anesthesia and any type of surgery, e.g. exposure to biohazardous materials

19.2. Anticipated Adverse Device Effects

The risks summarized below are anticipated during use of SCS as described in this protocol. The risks listed include those associated with the procedure to implant the SCS device system, the presence of the device (whether activated or not) within the body, and the use of SCS stimulation¹. Potential risks not already identified may exist.

The following anticipated adverse device effects (ADE) have been identified for the SCS device.

Very Common:

- Minor bruising

Common:

- Additional surgical procedure such as explant, revision, or reimplantation of the leads, extensions, or IPG, or revision of the IPG pocket
- Pain, including pain at IPG

¹ Note that some of these symptoms may be resolved or reduced by current steering, changing stimulation parameters, or by repositioning of the lead.

- Stimulation in non-target areas, which can include undesired sensations of pain, pressure, or numbness
- Undesired sensations at stimulation target areas, which can include feelings of pain, pressure, numbness, or dislike of paresthesia
- Overstimulation of tissue, which can include feeling sensations such as jolts or shocks, and potential injuries arising from this causing distraction or loss of muscle control (e.g. fall)

Less Common:

- Infection, such as cellulitis or subcutaneous abscess

Uncommon:

- Discomfort, which can include minor tenderness, uncomfortable awareness of the device, or anxiety
- Skin erosion, including pressure sores, over the device
- Swelling, including seroma, at the IPG site or other locations
- Weight gain or loss

Rare:

- Abnormal healing or failure to heal
- Allergic, immune, or inflammatory response or reaction to the presence of the device or its materials
- Burns due to charger misuse
- Death
- Dural tear with or without Cerebrospinal Fluid (CSF) leak
- Error during implantation of device, e.g. faulty connection of extension to the IPG, which can lead to additional surgery
- Headache
- Hematoma of a serious type, e.g. an epidural hematoma resulting in paralysis
- Hemorrhage requiring transfusion
- Inability to change stimulation, e.g. the remote control stops working
- Infection that is severe or life-threatening, such as epidural abscess, meningitis or sepsis
- Muscle spasms
- Musculoskeletal stiffness

- Nausea
- Nerve injury arising from the electrodes, which can result in symptoms such as unintended tingling, numbness, pain, loss of bladder or bowel control, weakness, or paralysis
- Pneumothorax, pneumocephalus, or injury to other tissues during surgery
- Seizure
- Stimulation-related symptoms in other body systems, e.g. changes to urinary function, priapism
- Tissue damage at implant site from exposure to MRI

19.3. Risks Associated with the Study Device(s)

There are no known incremental risks associated with the study device above those of market-available products.

19.4. Risks associated with Participation in the Clinical Study

The subject might find it difficult, uncomfortable, or tiresome to complete study visits, evaluate the device, and/or questionnaires.

19.5. Possible Interactions with Concomitant Medical Treatments

No possible interactions have been identified for use of the SCS system concomitant with any specific medications. However, there may be some risk that is unknown.

The following medical treatments should not be used while the SCS lead remains implanted.

Magnetic Resonance Imaging (MRI). The subject should not be exposed to Magnetic Resonance Imaging (MRI). Exposure to this diagnostic technology may result in dislodgement of the Stimulator or lead(s), heating of the Stimulator, damage to the Stimulator electronics and/or voltage induction through the leads or Stimulator which can cause an uncomfortable or “jolting” sensation.

Diathermy. SCS subjects should not have any form of diathermy either as treatment for a medical condition or as part of a surgical procedure. The high energy and heat generated by diathermy can be transferred through the stimulator system, causing tissue damage at the lead site and, possibly, severe injury or death. The Stimulator, whether it is turned on or off, may be damaged.

Implanted Stimulation Devices. Spinal cord stimulators may interfere with the operation of implanted sensing stimulators such as pacemakers or cardioverter defibrillators. The effects of implanted stimulation devices on neurostimulators are unknown.

Medical Devices/Therapies. The following medical therapies or procedures may turn stimulation off or may cause permanent damage to the Stimulator, particularly if used in close proximity to the device:

- Lithotripsy
- Electrocautery (See “Instructions for the Physician” in the Information for the Prescriber Manual)
- External defibrillation
- Radiation therapy
- Ultrasonic scanning
- High-output ultrasound

19.6. Risk Minimization Actions

Additional risks may exist. Risks can be minimized through compliance with this protocol, performing procedures in the appropriate hospital environment, adherence to subject selection criteria, close monitoring of the subject's physiologic status during research procedures and/or follow-ups and by promptly supplying BSC with all pertinent information required by this protocol.

19.7. Anticipated Benefits

The reported benefit of the Spectra WaveWriter SCS System may include:

- Reduction in the intensity of chronic low back pain
- Reduction in the intensity of chronic leg pain
- Reduction in overall chronic low back and leg pain
- Improvement in physical functioning (disability)
- Improvement in sleep
- Improvement in quality of life
- Improvement in depression
- Reduction in pain-related medication use
- Reduction in the occurrence of side-effects of pain-related medications accompanied by reduction in opioid use (e.g. sleep disturbances, constipation, reduction in mental acuity)

19.8. Risk to Benefit Rationale

The risk evaluation for the Spectra WaveWriter SCS System determined that all hazards attributed to the Spectra WaveWriter SCS System and overall remaining residual risks after implementations of the required mitigations have been evaluated. Based on the risk evaluation results, the benefit provided by the Spectra WaveWriter SCS System to treat chronic intractable pain of the trunk and limbs outweighs the remaining residual risk. As the

overall residual risk meets BSN’s criteria, the Spectra WaveWriter SCS System is acceptable for use in a clinical setting.

20. Safety Reporting

20.1. Reportable Events by investigational site to Boston Scientific

It is the responsibility of the investigator to assess and report to BSC any event which occurs in any of following categories:

- All Serious Adverse Events
- All Investigational Device Deficiencies
- Unanticipated Adverse Device Effects
- Non-serious device and/or procedure related adverse events
- New findings/updates in relation to already reported events

When possible, the medical diagnosis should be reported as the Event Term instead of individual symptoms.

If it is unclear whether or not an event fits one of the above categories, or if the event cannot be isolated from the device or procedure, it should be submitted as an adverse event and/or device deficiency.

Any AE event required by the protocol, experienced by the study subject after informed consent and once considered enrolled in the study (as defined in study subject classification section), whether during or subsequent to the procedure, must be recorded in the eCRF.

Underlying diseases are not reported as AEs unless there is an increase in severity of frequency during the course of the investigation. Death should not be recorded as an AE, but should only be reflected as an outcome of ONE (1) specific SAE (see Table 20.2-1 for AE definitions).

Refer to Section 19 for the known risks associated with the study device(s).

20.2. Definitions and Classification

Adverse event definitions are provided in Table 20.2-1. Administrative edits were made on the definition of serious adverse event from ISO 14155 and MEDDEV 2.7/3 for clarification purposes.

Table 20.2-1: Safety Definitions

| Term | Definition |
|---|--|
| Adverse Event (AE) Ref: ISO 14155 | Any untoward medical occurrence, unintended disease or injury, or any untoward clinical signs (including an abnormal laboratory finding) in subjects, users or other persons, whether or not related to the investigational medical device. NOTE 1: This includes events related to the investigational medical device or comparator. |

Table 20.2-1: Safety Definitions

| Term | Definition |
|--|---|
| 
Ref: MEDDEV 2.7/3
 | 
NOTE 2: This definition includes events related to the procedures involved. NOTE 3: For users or other persons, this definition is restricted to events related to the investigational medical device.
 |
| 
Adverse Device Effect (ADE)
 
Ref: ISO 14155
 
Ref: MEDDEV 2.7/3
 | 
Adverse event related to the use of an investigational medical device
 
NOTE 1: This includes any adverse event resulting from insufficiencies or inadequacies in the instructions for use, the deployment, the implantation, the installation, the operation, or any malfunction of the investigational medical device.
 
NOTE 2: This definition includes any event resulting from use error or intentional abnormal use of the investigational medical device.
 |
| 
Serious Adverse Event (SAE)
 
Ref: ISO 14155
 
Ref: MEDDEV 2.7/3
 | 
Note: This definition meets the reporting objectives and requirements of ISO 14155 and MEDDEV 2.7/3.
 
Adverse event that:
 
a) Led to death,
 
b) Led to serious deterioration in the health of the subject as defined by either:
 
 1) a life-threatening illness or injury, or 2) a permanent impairment of a body structure or a body function, or 3) in-patient hospitalization or prolongation of existing hospitalization, or 4) medical or surgical intervention to prevent life-threatening illness or injury or permanent impairment to a body structure or a body function 
c) Led to fetal distress, fetal death, or a congenital abnormality or birth defect.
 
NOTE 1: Planned hospitalization for a pre-existing condition, or a procedure required by the clinical investigational plan, without a serious deterioration in health, is not considered a serious adverse event.
 |
| 
Serious Adverse Device Effect (SADE)
 
Ref: ISO 14155
 
Ref: MEDDEV 2.7/3
 | 
Adverse device effect that has resulted in any of the consequences characteristic of a serious adverse event.
 |
| 
Unanticipated Adverse Device Effect (UADE)
 
Ref: 21 CFR Part 812
 | 
Any serious adverse effect on health or safety or any life-threatening problem or death caused by, or associated with, a device, if that effect, problem, or death was not previously identified in nature, severity, or degree of incidence in the investigational plan or application (including a supplementary plan or application), or any other unanticipated serious problem associated with a device that relates to the rights, safety, or welfare of subjects.
 |
| 
Device Deficiency
 
Ref: ISO 14155
 | 
An inadequacy of an investigational medical device related to its identity, quality, durability, reliability, safety or performance. This may include malfunctions, use error, or inadequacy in the information supplied by the manufacturer.
 |

Table 20.2-1: Safety Definitions

| Term | Definition |
|----------------------|------------|
| Ref: MEDDEV 2.7/3 | |

Abbreviations: IRB=Institutional Review Board

Underlying diseases are not reported as AEs unless there is an increase in severity or frequency during the course of the investigation. Death should not be recorded as an AE, but should only be reflected as an outcome of a specific SAE.

Any AE experienced by the study subject after informed consent, whether during or subsequent to the procedure, must be recorded in the eCRF.

Refer to Section 19 for the known risks associated with the study device(s).

NOTES:

1. For the purposes of this study, hospitalization is defined as any in-patient admission.
2. Hospitalizations occurring for the purpose of performing a planned procedure as per routine care such as implant procedures, or follow-up visits, are not to be reported as a SAE. However, complications or adverse events that occur during the planned procedure should be reported as (S)AEs if they meet the protocol specified definitions.
3. Elective/planned hospitalization(s) need not be reported as an SAE. However, complications or adverse events that occur during an elective/planned hospitalization, should be reported as (S)AEs if they meet the protocol specified definitions.
4. In the event of subject death during the conduct of the study, efforts should be made to perform an autopsy.
5. Sensations or side effects that occur during the programming session should not be reported as AEs. However, undesired sensations or side effects caused by the final programming parameters (including active contact, pulse width, frequency, and amplitude) that persist or occur after the completion of the programming should be reported as AEs.
6. Lack of efficacy/decreased therapeutic response should not be reported as AEs. Clinical sequelae, other than pain, that occur as a result of lack of efficacy/decreased therapeutic response should be reported as AEs
7. Clinically significant worsening of the pattern of intensity or distribution of Baseline pain symptoms should be reported as an AE.
8. Device deficiencies, including, but not limited to device/lead migrations, which are not associated with an adverse clinical outcome should only be reported as device deficiencies. However, if a device deficiency precipitates an AE, the AE should be reported in the *Adverse Event* eCRF and the device deficiency should be documented in the *Device Deficiency* eCRF.

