13.2. Study Assessments

13.2.1. Adverse Events

Adverse event evaluation will be conducted to identify adverse events occurring during the study and classify them in regards to seriousness, relationship to the implant procedure and/or device, action taken and outcome. Safety events will be reported as specified in Table 20.4-1.

All device and procedure related non-serious adverse events, all serious adverse events, and unanticipated adverse events will be collected from the time of consent through the end of the study.

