20.4. Investigator Reporting Requirements

The communication requirements for reporting to BSC are as shown in Table 20.4-1.

Table 20.4-1: Investigator Reporting Requirements

| Event Classification | Communication Method | Communication Timeline post-market studies** (MEDDEV 2.12/2: GUIDELINES ON A MEDICAL DEVICE VIGILANCE SYSTEM) |
|-------------------------------------|---|---|
| Unanticipated Adverse Device Effect | Complete AE eCRF page with all available new and updated information. | 
 • Within 1 business day of first becoming aware of the event. • Terminating at the end of the study |
| Serious Adverse Event | Complete AE eCRF page with all available new and updated information. | 
 • Within 10 business days after becoming aware of the event or as per local/regional regulations. Reporting required through the end of the study |

Table 20.4-1: Investigator Reporting Requirements

| Event Classification | Communication Method | Communication Timeline post-market studies** (MEDDEV 2.12/2: GUIDELINES ON A MEDICAL DEVICE VIGILANCE SYSTEM) |
|---|---|--|
| | Provide all relevant source documentation (unidentified) for reported event upon request of the sponsor. | 
 • When documentation is available |
| Serious Adverse Device Effects | Complete AE eCRF page with all available new and updated information. | 
 • Within 2 business days of first becoming aware of the event or as per local/regional regulations. • Reporting required through the end of the study |
| | Provide all relevant source documentation (unidentified) for reported event | 
 • When documentation is available |
| Device Deficiencies (including but not limited to failures, malfunctions, and product nonconformities) Note: Any Investigational Device Deficiency that might have led to a serious adverse event if a) suitable action had not been taken or b) intervention had not been made or c) if circumstances had been less fortunate is considered a reportable event. | Complete Device Deficiency eCRF with all available new and updated information. | 
 • Within 2 business days of first becoming aware of the event. • Reporting required through the end of the study |

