| Adverse Device Effects | Complete AE eCRF page, which contains such information as date of AE, treatment of AE resolution, assessment of seriousness and relationship to the device. | 
 • In a timely manner (e.g. recommend within 30 business days) after becoming aware of the information • Reporting of Adverse events which are device/procedure related will be required through the end of the study. |

Abbreviations: AE=adverse event; CRF=case report form; IDE=Investigational Device Exemption; UADE=unanticipated adverse device effect

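### Section 20.2 Note 3 exempts planned admissions more widely than the plan's own SAE definition, so some new events can be left out of the SAE rate

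*Combined protocol and SAP*

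**What the plan says.** Two passages of Section 20.2 govern planned admissions.

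- **Table 20.2-1, SAE definition.** Criterion b3 makes an adverse event serious if it led to "in-patient hospitalization or prolongation of existing hospitalization". The table's own NOTE 1 takes out a limited class: "Planned hospitalization for a pre-existing condition, or a procedure required by the clinical investigational plan, without a serious deterioration in health".
- **Numbered notes below the table.** Note 1 counts every in-patient admission as a hospitalization. Note 2 exempts admissions for planned routine-care procedures such as the implant. Note 3 then adds: "Elective/planned hospitalization(s) need not be reported as an SAE". Its second sentence says that "complications or adverse events that occur during an elective/planned hospitalization, should be reported as (S)AEs" if they meet the protocol's definitions.

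Section 7.5 lists the rate of all SAEs among the primary safety parameters. Section 13.2.1 sets the collection rule: "All device and procedure related non-serious adverse events, all serious adverse events, and unanticipated adverse events will be collected". Section 20.1 gives sites a matching list, in which non-serious events are reportable only if related to the device or procedure.

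**The concern.** The notes should explain the definition, but Note 3 changes it. Anyone applying the table asks why the subject was admitted and whether health had deteriorated. Anyone applying Note 3 asks only whether the admission was elective or planned. For some events the two questions give different answers, and the protocol does not say which text prevails.

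The situation is plausible in this study. Section 19.2 lists explant, revision and reimplantation surgery as a common anticipated device effect. Section 11.16.1 refers sites to Section 20 to decide how revisions and replacements are assessed as adverse events. Where such surgery involves an in-patient stay, it may well be booked ahead.

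At stake are the SAE rate and its consistency between sites. The study has a single arm, so no concurrent control group would share the same inconsistency.

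**Working it through.** The protocol states no expected SAE rate or count, so there is no figure to reproduce. The check sets the passages against each other.

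**Step 1. Compare the two exemptions.**

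| Question | Table 20.2-1, NOTE 1 | Section 20.2, Note 3 |
|---|---|---|
| Which planned admissions? | Pre-existing condition, or procedure required by the plan | Any elective or planned admission |
| Condition on health? | No serious deterioration | None stated |
| What is brought back? | Not applicable | Events arising during the stay |

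**Step 2. Is Note 3 only a restatement of Note 2?** No. Note 2 already covers the implant and other routine planned procedures, so Note 3 reaches beyond them.

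**Step 3. Run a test case through both texts.** Take an event that begins after consent, meets no seriousness criterion except b3, and is treated by a scheduled in-patient admission.
- Criterion b3 with Note 1: serious, because any in-patient admission counts and booked stays are not separated from urgent ones.
- Table NOTE 1: no exemption, because the condition is new and the admission is not for a procedure the plan requires.
- Note 3, first sentence: the planned hospitalization need not be reported as an SAE.
- Note 3, second sentence: no help, because the event led to the admission and did not arise during it.

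The event is an SAE under the table and may go unreported as one under Note 3.

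**Step 4. Follow the consequence.**
- *Device-related event.* As a serious adverse device effect, Table 20.4-1 requires it "Within 2 business days of first becoming aware of the event or as per local/regional regulations". As a non-serious adverse device effect, the same table asks for it "In a timely manner (e.g. recommend within 30 business days) after becoming aware of the information". It is still collected, but in a different class and on a looser timeline.
- *Unrelated event.* Once non-serious, it is on neither the Section 13.2.1 list nor the Section 20.1 list. However, Section 20.2 also says that any AE after consent must be recorded in the eCRF, and Section 11.2.2 says any adverse event after enrolment is documented. Section 20.1 limits its own recording sentence to AEs the protocol requires. Whether the event reaches the database is therefore unsettled.

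**Step 5. Size.** Let f be the share of SAEs under the table that qualify only through a planned admission outside NOTE 1. If every site used Note 3 for all of them, reported count = (1 − f) × count under the table, so the relative understatement equals f. As an assumption only, f from 0 to 0.30 gives:
- f = 0: 1 − 0 = 1.00, understatement 0%.
- f = 0.30: 1 − 0.30 = 0.70, understatement 30%.

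The documents give no value for f, so this range shows the form of the effect and is not an estimate.

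**The case against.** The strongest reply is that Note 3 excuses the hospitalization and not the adverse event behind it. On that reading an elective stay is not itself an SAE, seriousness is still set by the table, and Section 20.1 still requires all SAEs. The words are also permissive: a site need not report, but may. This stands against the inference that such events *will* drop out of the SAE rate. The documents support only that they *can*. It does not remove the problem, because a permissive rule is what allows two sites to differ while both comply.

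Other limits also stand:
- Events that led to death, life-threatening illness or permanent impairment, or that needed intervention to prevent such illness or impairment (b4), remain SAEs however the admission was arranged. A device-site infection may qualify this way.
- Notes 6 and 8 keep loss of efficacy, and device deficiencies without an adverse clinical outcome, out of AE reporting. Many revisions may therefore never raise the question.
- A reader might infer that unrelated events are simply not collected. The general recording sentence in Section 20.2 prevents that conclusion. Section 20.1 also tells sites to submit an event as an AE and/or device deficiency when its category is unclear, though this does not make it an SAE.
- A reader might contrast this with a 10-business-day SAE deadline. Table 20.4-1 does give 10, but Section 23.4 treats failure to report an SAE within 2 business days as a possible reason for suspending or terminating a site. The 10-day figure is not a firm base.
- Much of the statistical section is redacted, so how SAE rates are derived cannot be seen.

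**Conclusion.** The inconsistency is real, and it is confined to new post-consent events whose only seriousness criterion is in-patient admission and which are treated by a planned admission. For these, Note 3 permits an omission that Table 20.2-1 does not, so the SAE rate can be understated and can vary with the text a site follows. A device-related event of this kind would be misclassified rather than lost. An unrelated one might not be reported.

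The size is unknown. It depends on how many events meet that description and how many sites rely on Note 3, and it could be close to zero. No numerical understatement can be claimed from the documents. The effect is on safety classification, not on the primary endpoint. The point still merits correction because the plan contradicts its own definition of a stated safety parameter and the repair is simple.

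**What to change.** Replace the first sentence of Note 3 with the table's limits: "Planned hospitalization for a pre-existing condition, or a procedure required by the clinical investigational plan, without a serious deterioration in health", need not be reported as an SAE. Then add: *A planned or elective in-patient admission for an adverse event that began or worsened after consent is judged by the SAE definition in Table 20.2-1.* Keep the existing sentence on events arising during the stay.

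Do not add a requirement that the admission was planned before consent. The table's NOTE 1 has no such condition. An admission booked after consent for an unchanged pre-existing condition would then be exempt under the table but not under the note, which is a new mismatch.

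The cost is a small protocol amendment. Under Section 14, a revision that affects subject safety or the integrity of the data needs IRB approval before it takes effect. The reported SAE rate may rise slightly. No visit, procedure or assessment changes.

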11.9. Programming Period (Up to 70 days following the Activation Visit)

Following device activation, subjects’ device will be optimized to achieve effective therapy during the Programming Period of up to 70 days post-activation.

During this period, subjects may return as many times as needed (unscheduled visits) for optimization of programming.

Information regarding programming parameters and device information may be collected and documented.

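### The AE exclusion for programming sessions (section 20.2, Note 5) leaves lasting harm from a setting tried and not kept unreportable as written, and does not expressly preserve SAE or UADE reporting

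*Combined protocol and SAP*

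**What the plan says.** Note 5 in section 20.2 has two sentences. The first is a general exclusion: "Sensations or side effects that occur during the programming session should not be reported as AEs". The second is the only exception, and it covers "undesired sensations or side effects caused by the final programming parameters (including active contact, pulse width, frequency, and amplitude) that persist or occur after" the programming is complete.

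Three other provisions set the general rule:

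- Section 20.1 lists the categories a site must report. The first is "All Serious Adverse Events"; UADEs and non-serious device- or procedure-related events are listed separately.
- Section 13.2.1 states: "All device and procedure related non-serious adverse events, all serious adverse events, and unanticipated adverse events will be collected from the time of consent", and continues to the end of the study.
- Section 20.2, just above the notes, states: "Any AE experienced by the study subject after informed consent, whether during or subsequent to the procedure, must be recorded in the eCRF".

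Section 7.5 makes the rates of these same categories the safety parameters of the study.

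**The concern.** Leaving out the passing sensations of test stimulation is sensible. The difficulty is that the first sentence has no limit by seriousness, injury or duration, and the second restores events by cause (the final settings) and not by clinical outcome. A site that follows Note 5 to the letter could therefore omit an event that sections 13.2.1 and 20.1 require, and the plan does not say which provision prevails.

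Programming is also frequent. Section 11.9 says that "subjects may return as many times as needed (unscheduled visits) for optimization of programming" over a period of up to 70 days. Sections 11.12 to 11.15 provide for programming as needed at the 3-, 6- and 9-month and Year 1 visits, and section 11.16 allows unscheduled visits throughout. What is at stake is the completeness of the device- and stimulation-related AE counts, and possibly of the SAE count, in a single-arm study whose safety parameters are simple occurrence rates.

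**Working it through.** No arithmetic applies, and the plan states no figure to reproduce. The check is to apply the text to each kind of event.

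| Event | Note 5, sentence 1 | Note 5, sentence 2 | Sections 13.2.1, 20.1 and general rule of 20.2 | Result |
|---|---|---|---|---|
| A. Passing, non-serious sensation in the session | Excluded | Not restored | Arguably not an AE at all | Intended exclusion; no problem |
| B. Effect of the final settings that persists or appears afterwards | Excluded if it began in the session | Restored | Required | Consistent |
| C. Effect that begins in the session under a setting later dropped, and lasts | Excluded | Not restored, because the cause is not the final parameters | Required if it is an AE related to device or procedure | Conflict |
| D. In-session event that meets the SAE definition and is outside B | Excluded on a literal reading | Not restored | Required | Conflict, softened by 20.1 |
| E. Effect of a dropped setting that first appears after the session | Not covered | Not restored | Required | Reportable under the general rule |

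**Case C.** It might be said that an effect which outlasts the session is no longer one that occurs during it. But sentence 2 deals with persistence directly and limits it to "undesired sensations or side effects caused by the final programming parameters". The natural inference is that persistence from any other setting was not meant to be restored.

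**Case D.** In Table 20.2-1 the SAE is defined as a kind of adverse event, and the SADE as a kind of adverse device effect, which is itself an adverse event. Table 20.4-1 sends UADEs, SAEs, SADEs and ADEs all through the AE eCRF page. An event that is not to be reported as an AE thus has no separate form. The UADE definition does not rest on the AE definition, so for UADEs the conflict lies in the shared form and the missing exemption.

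**Comparison with the neighbouring notes.** Notes 2 and 3 exclude planned hospitalizations but bring back complications that meet the protocol's (S)AE definitions. Note 6 brings back clinical sequelae other than pain, and Note 8 brings back an AE that a device deficiency precipitates. Each restores by clinical outcome. Note 5 restores by which setting was the cause.

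**Whether such events are foreseeable.** Section 19.2 lists overstimulation under Common and says it may involve "potential injuries arising from this causing distraction or loss of muscle control (e.g. fall"). It lists seizure under Rare. Neither entry is tied to programming sessions, and the plan gives no frequency for either event within a session.

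**The case against.** The best case for the plan concerns serious events. Note 5 speaks of AEs, whereas Notes 2 and 3 name SAEs when they mean them and so need a carve-back. Section 20.1 lists SAEs and UADEs apart from non-serious related events, so Note 5 can be read as trimming only the non-serious category. Section 20.1 also tells sites to submit an event when its category is unclear or when it cannot be isolated from the device or procedure. This has weight: a careful investigator would probably report a serious in-session event. It does not settle the matter, because the SAE definition is built on the AE definition and nothing says that 20.1 overrides Note 5. Nor does it help case C, where Note 5 is not unclear.

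A reader might also infer more than the documents support:

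- That Note 5 bars every side effect of programming. It does not; cases B and E remain reportable.
- That injury from overstimulation is common. The Common label attaches to overstimulation, which includes jolts and shocks; injuries are mentioned only as potential, with no frequency of their own.
- That a seizure in a session is automatically an SAE. It must meet a Table 20.2-1 criterion, and one that resolves in the session may not. Permanent impairment and admission usually outlast the session, so the class that is serious yet over by its end is narrow.
- That listed effects such as overstimulation or seizure are wholly excluded. Only in-session occurrences are in question.

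Finally, a rule to report anything that persists, with no threshold, would sweep in brief tingling after a discarded setting. That objection stands and shapes the fix.

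**Conclusion.** The point holds in a limited form. As written, lasting harm from a setting tested and not kept is not reportable under Note 5, although sections 13.2.1 and 20.2 would require it if it is a device- or procedure-related AE. Reporting of in-session events that meet the SAE or UADE definition is not expressly preserved; here the conflict is weaker, because 20.1 offers a partial safeguard.

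If any qualifying events are left out, the bias in the section 7.5 rates is downward. A reader might infer that the rates are in fact understated, but the documents do not show that any such event will occur or that sites will apply Note 5 literally. The supportable statement is that the rates of related AEs, and possibly of SAEs, may be understated by an amount that cannot be derived. The primary endpoint, a pain responder rate with an opioid condition, is not touched.

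This rests on the literal wording and on the visible text. Parts of section 12 are redacted and could bear on the safety analysis.

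**What to change.** Keep the exclusion for transient sensations and add one sentence to Note 5, in the style of Notes 2 and 3:

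*However, any event during a programming session that meets the SAE or UADE definition, or that results in injury or an untoward clinical effect continuing after the session (other than brief residual sensation), should be reported as an (S)AE, whether caused by a tested or a final setting.*

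This closes cases C and D, leaves A excluded, and brings Note 5 into line with the outcome-based exceptions in Notes 2, 3, 6 and 8. The words on brief residual sensation keep trivial after-effects out. It is a reporting rule and changes no clinical management. The cost is one sentence, slightly more AE entries, and a possibly slightly higher stimulation-related AE rate.
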